12 STUDY MANAGEMENT

12.1 Monitoring

The Investigator will be responsible for preparing and maintaining adequate and accurate source documents (medical records, ECGs, raw data collection forms, etc.) designed to record all observations and other pertinent data for each subject treated with the study drug. The Investigator will allow representatives of the Sponsor, contract designees, authorized regulatory authority inspectors, and the Institutional Review Board (IRB)/Independent Ethics Committee (IEC) to have direct access to all documents pertaining to the study. The Investigator is to immediately notify the Sponsor of any regulatory authority inspections. The Investigator will be informed about the outcome of any Sponsor audit.

This study will be monitored regularly, by or under supervision of a monitor from the Sponsor. The frequency of monitoring visits will be agreed upon by the Sponsor's representative and the study site.

Monitoring visits will take place on a regular basis according to the enrollment rate and number of subjects enrolled at each investigational site. During these visits, the monitor will check the completion of the CRF/eCRF entries, compliance with the study protocol and with Good Clinical Practice - International Conference on Harmonization (GCP-ICH), and their agreement with the source data. The monitor will also verify the correct use of the study drug. At a final visit, the monitor will check all remaining material including the remaining quantities of the study drug and will organize their return to the Sponsor or designee. At each visit, the Investigator and staff will be expected to cooperate with the Sponsor's representative(s) for the purposes of review and verification of protocol compliance, AE reporting, CRFs/eCRFs, source documents, clinical supplies and inventory records, and any additional records as may have been previously arranged between the Investigator and the Sponsor's representative(s).

The Investigator and/or other designated study personnel are expected to contact the Sponsor with any study concerns and/or questions. Contact information is provided in the Study Reference Manual for the site.

12.2 Protocol Amendments

The Sponsor may propose to amend this protocol at any time.

No change to the protocol will be implemented until the Sponsor and the IRB/IEC have reviewed and approved the amendment.

In the event of an emergency, the Investigator shall implement any medical procedures deemed appropriate for subject safety. All such procedures must have written documentation and be promptly reported to the Sponsor.

12.3 Protocol Deviations

A protocol deviation is any change, divergence, or departure from the IRB/IEC approved protocol (intentional or unintentional). Protocol deviations are to be reported to the IRB/IEC according to the IRB/IEC guidelines.

12.4 Withdrawal of Subjects

Withdrawn subjects are those who do not complete all evaluations and procedures outlined in the protocol. A subject will be considered to have discontinued prematurely if he/she withdraws after being randomized and prior to completing Visit 6 (Final Visit). Subjects who discontinue taking study drug for any reason for greater than 5 consecutive days must also be withdrawn from the study. Subjects may be withdrawn from the study because of any of the following:

- **Adverse Event:** An AE that, in the opinion of the Investigator or Sponsor, suggests that continued participation in the study is not in the subject's best interest for safety reasons (also see [Section 10](#)). All AEs that are present when the subject withdraws from the study will be followed as described in [Section 9.7.4](#).
- **Medical Condition:** Any medical condition that, in the Investigator's judgment, would increase the risk or interfere with the evaluation of study objectives.
- **Lost to Follow-up:** As per the comprehensive lost to follow-up guidance document that will be submitted to the IRB/IEC with the clinical protocol.
- **Subject Request:** Subject requests for any reason to be withdrawn or withdraws his/her consent.
- **Protocol Deviation:** A subject may be withdrawn from the study at the discretion of the Investigator or Sponsor due to poor compliance with protocol requirements that may compromise the study results or subject safety.
- **Enrollment in Another Study:** Enrollment in other protocols involving research drugs, medical devices, or surgeries.
- **Other Anti-spasticity Treatment:** Starting any other pharmacological anti-spasticity treatment during the study.

- **Relapse:** Subjects who experience an acute MS exacerbation/relapse (symptoms including but not limited to visual disturbance, dizziness, tingling, or extreme fatigue lasting greater than 24 hours and occurring at least 30 days after a previous relapse) requiring immediate therapy or adjustment in disease-modifying medication dose (eg, oral or intravenous high-dose steroid therapy). Upon resolution of symptoms, the subject may choose to be assessed for entry into the subsequent open-label extension study (Study OS440-3005).
- **Other:** Other reasons include but are not limited to: Investigator decision that it is in the subject's best interest to be withdrawn, administrative reasons, relocation of subject, etc. If a subject or the partner of a subject becomes pregnant during the study, the subject will be withdrawn from the study and followed through conclusion of the pregnancy (see [Section 9.7.5](#)).

When possible, a decision to discontinue a subject from the study should first be discussed with the Sponsor's Medical Monitor. If a subject is prematurely discontinued after randomization and prior to the final scheduled visit, every effort should be made to perform all of the Visit 6 assessments (Table 1). The reason(s) for early withdrawal must be recorded in the CRF/eCRF. Subjects withdrawn from the study will not be replaced.

12.5 Termination of the Study

The study may be terminated at any time at the request of the Sponsor or a regulatory authority, with proper and timely notification of all parties concerned. The IRB/IEC will be informed promptly and the Sponsor or the Investigator will supply reason(s) for the termination or suspension, as specified by the applicable regulatory requirements. Otherwise, the study is considered terminated upon completion of all subject treatments and evaluations.

12.6 Publication Policy

The data obtained in this study are the property of the Sponsor, who will make reasonable efforts to assure that the results are published in a peer-reviewed journal. As some of the information concerning the investigational product and development activities at the Sponsor may be of a strictly confidential nature, any manuscript or other presentation of data must first be reviewed by the Sponsor before its submission.

13 ETHICS

13.1 Conduct of the Study

This study will be conducted in accordance with the ICH Harmonized Tripartite Guideline for GCP, 1997; the US Title 21 CFR parts 50, 56, and 312; and the ethical principles that have their origin in the Declaration of Helsinki. The study will not begin until all of the requirements of the appropriate regulatory authorities have been fulfilled.

13.2 Institutional Review Boards and/or Independent Ethics Committees

This protocol (and any changes), all consent forms, and subject consent procedures must be reviewed and approved by a properly constituted IRB/IEC. The information presented to the

IRB/IEC at the time initial approval is sought must include any plans for subject recruitment that involve advertising or other direct contact with potential subjects outside of the doctor-subject relationship. A letter of approval issued by the IRB/IEC must be sent to the Sponsor prior to initiation of the study. Any changes made to the protocol must be approved by the IRB/IEC prior to implementation, except where needed to eliminate a potential imminent safety hazard to the subject. In this case, immediate implementation may take place followed by IRB/IEC approval. Review and approval by the IRB/IEC for continuation of the study must take place at least once a year.

13.3 Written Informed Consent

The Investigator or designee will explain the nature of the study, its purpose and associated procedures, the expected duration, and the potential benefits and risks of participation to each subject prior to his/her entry into the study (ie, before examinations and procedures associated with selection for the study are initiated). Each subject will have ample opportunity to ask questions and will be informed about the right to withdraw from the study at any time without any disadvantage and without having to provide reasons for this decision.

Following this informative discussion, the subject will be asked if he/she is willing to sign a statement of informed consent. Only subjects who voluntarily sign the ICF may enter the study. The ICF must be reviewed and approved by the Sponsor and the IRB/IEC prior to its use.

The original signed ICF will remain in the Investigator's files. The Investigator or designee will indicate in each subject's source documents that he/she has informed the subject about the study and its procedures, the subject has signed and dated the ICF, and the subject has been given a copy of the signed ICF. The Investigator or designee will inform subjects of any new information that may be relevant to the subject's willingness to continue in the study.

13.4 Subject Confidentiality

The Sponsor ensures that the following have permission to review all study-related documents: monitor, auditor, IRB/IEC, and regulatory authorities. The subject's identity and study-related records will remain confidential throughout the duration of the study data collection and reporting process.

A unique subject identification code will be assigned to each potential study subject. The identification code protects the subject's identity and is used in lieu of the subject's name when reporting subject data. The data will always maintain the confidentiality of the subject.

The Investigator or designee will review the subject data, which will be referenced using the subject identifier. At the conclusion of the study, the data obtained may be presented to regional regulatory authorities but the subject's identity will not be revealed. In addition, if any clinical data obtained from the study are published in scientific journals or presented at scientific meetings, the subject's identity will not be revealed.

13.5 Records Retention

The Investigator must maintain essential study documents (protocol and amendments, source documentation corresponding to all information contained in the CRFs/eCRFs, signed ICFs, relevant correspondence, and all other supporting documentation) until at least 2 years after the last approval of a marketing application in an ICH region and until there are no pending or contemplated marketing applications in an ICH region, or at least 2 years after the formal discontinuation of clinical development of the investigational product. These documents should be retained for a longer period if required by the applicable regulatory requirements or the hospital, institution, or private practice in which the study is being conducted. Subject identification codes (subject names and corresponding study numbers) will be retained for this same time period. Custody of the records may be transferred to another responsible party, acceptable to the Sponsor, who agrees to abide by the retention policies. Written notice of transfer must be submitted to the Sponsor. The Investigator must contact the Sponsor prior to disposing of any study records.

13.6 Financing

Funding for this study will be agreed between the Investigator and the Sponsor and will be confirmed in writing before the study starts.

Completion of Financial Disclosure Forms will be required before the study starts. Any additions to the primary site personnel will necessitate the completion of new Financial Disclosure Forms. This information will also be collected at site closure and 1 year after the completion of the study.

14 QUALITY CONTROL AND QUALITY ASSURANCE

The Sponsor and Investigator will take all steps possible to ensure the accuracy, consistency, completeness, and reliability of the data, including participating in an Investigator meeting and/or site initiation visit, routine site monitoring, review of CRFs/eCRFs against source documents, and quality control checks.

In addition, a representative from the Sponsor's Clinical Quality Assurance Department may conduct periodic audits of the study processes, including, but not limited to, auditing the clinical site, laboratories, vendors and CROs, the clinical database, and the final study report.

15 DATA HANDLING AND RECORD KEEPING

This study will use web-based, electronic case report forms (eCRFs) developed through a validated, Electronic Records/Electronic Signatures-compliant platform (US Title 21 CFR Part 11). The Sponsor's Clinical Data Management department or designee will create the eCRFs and corresponding clinical database based on the final protocol.

All site personnel who will be using this system will receive formal training on the system, after which each person will be issued a unique username and password. Only the person who owns the username and password will enter the system using that username and password. For data

security reasons and to be in compliance with regulatory guidelines, usernames and passwords are not transferable.

The Investigator is responsible for all data entered via the remote data capture (RDC) system eCRFs and must confirm the accuracy of the data by electronically approving (signing) the eCRFs. This responsibility includes the timely completion and accuracy of the data entered into the eCRFs by their site personnel as well as the review and approval of some data entered directly into the database (eg, clinical laboratory results) by an external vendor. The Sponsor will review the database to identify data errors or inconsistencies, which will be posted in the RDC system as queries for resolution. In addition, the Sponsor may make obvious corrections to the data in the database (eg, obvious errors in dates).

Appendix 1. Modified Ashworth Scale

Score	Modified Ashworth Scale
0	No increase in muscle tone
1	Slight increase in muscle tone, manifested by a catch and release or by minimal resistance at the end of the range of motion when the affected part(s) is moved in flexion or extension /abduction or adduction, etc.
1+	Slight increase in muscle tone, manifested by a catch, followed by minimal resistance throughout the remainder (less than half) of the ROM (range of movement).
2	More marked increase in muscle tone through most of the ROM, but affected part(s) easily moved.
3	Considerable increase in muscle tone, passive movement difficult.
4	Affected part(s) rigid in flexion or extension (abduction or adduction, etc.)

Source: [Bohannon and Smith 1987](#)

Scoring: (Total Numeric-transformed mAS score)

Ashworth Score	0	1	1+	2	3	4
	↓	↓	↓	↓	↓	↓
Numerical Score	0	1	2	3	4	5

Numerical Score

Upper Extremities:

Shoulder

Elbow

Wrist

Numerical Total:

R	L

Lower Extremities:

Hip

Knee

Ankle

Numerical Total:

R	L

Appendix 2. Expanded Disability Status Score

0.0	Normal neurological exam (all grade 0 in all Functional System [FS] scores*).
1.0	No disability, minimal signs in one FS* (i.e., grade 1).
1.5	No disability, minimal signs in more than one FS* (more than 1 FS grade 1).
2.0	Minimal disability in one FS (one FS grade 2, others 0 or 1).
2.5	Minimal disability in two FS (two FS grade 2, others 0 or 1).
3.0	Moderate disability in one FS (one FS grade 3, others 0 or 1) or mild disability in three or four FS (three or four FS grade 2, others 0 or 1) though fully ambulatory.
3.5	Fully ambulatory but with moderate disability in one FS (one grade 3) and one or two FS grade 2; or two FS grade 3 (others 0 or 1) or five grade 2 (others 0 or 1).
4.0	Fully ambulatory without aid, self-sufficient, up and about some 12 hours a day despite relatively severe disability consisting of one FS grade 4 (others 0 or 1), or combination of lesser grades exceeding limits of previous steps; able to walk without aid or rest some 500 meters.
4.5	Fully ambulatory without aid, up and about much of the day, able to work a full day, may otherwise have some limitation of full activity or require minimal assistance; characterized by relatively severe disability usually consisting of one FS grade 4 (others or 1) or combinations of lesser grades exceeding limits of previous steps; able to walk without aid or rest some 300 meters.
5.0	Ambulatory without aid or rest for about 200 meters; disability severe enough to impair full daily activities (e.g., to work a full day without special provisions); (Usual FS equivalents are one grade 5 alone, others 0 or 1; or combinations of lesser grades usually exceeding specifications for step 4.0).
5.5	Ambulatory without aid for about 100 meters; disability severe enough to preclude full daily activities; (Usual FS equivalents are one grade 5 alone, others 0 or 1; or combination of lesser grades usually exceeding those for step 4.0).
6.0	Intermittent or unilateral constant assistance (cane, crutch, brace) required to walk about 100 meters with or without resting; (Usual FS equivalents are combinations with more than two FS grade 3+).
6.5	Constant bilateral assistance (canes, crutches, braces) required to walk about 20 meters without resting; (Usual FS equivalents are combinations with more than two FS grade 3+).
7.0	Unable to walk beyond approximately 5 meters even with aid, essentially restricted to wheelchair; wheels self in standard wheelchair and transfers alone; up and about in wheelchair some 12 hours a day; (Usual FS equivalents are combinations with more than one FS grade 4+; very rarely pyramidal grade 5 alone).

7.5	Unable to take more than a few steps; restricted to wheelchair; may need aid in transfer; wheels self but cannot carry on in standard wheelchair a full day; May require motorized wheelchair; (Usual FS equivalents are combinations with more than one FS grade 4+).
8.0	Essentially restricted to bed or chair or perambulated in wheelchair, but may be out of bed itself much of the day; retains many self-care functions; generally has effective use of arms; (Usual FS equivalents are combinations, generally grade 4+ in several systems).
8.5	Essentially restricted to bed much of day; has some effective use of arm(s); retains some self-care functions; (Usual FS equivalents are combinations, generally 4+ in several systems).
9.0	Helpless bed patient; can communicate and eat; (Usual FS equivalents are combinations, mostly grade 4+).
9.5	Totally helpless bed patient; unable to communicate effectively or eat/swallow; (Usual FS equivalents are combinations, almost all grade 4+).
10.0	Death due to MS.

FS = Functional System

* Excludes cerebral function grade 1.

Note 1: EDSS steps 1.0 to 4.5 refer to patients who are fully ambulatory and the precise step number is defined by the FS score(s). EDSS steps 5.0 to 9.5 are defined by the impairment to ambulation and usual equivalents in FS scores are provided.

Note 2: EDSS should not change by 1.0 step unless there is a change in the same direction of at least one step in at least one FS.

Appendix 3. Clinical Global Impression of Change Scale

Based on your assessment of the subject since Visit 2 (Baseline), please rate the change in overall global functional performance of the subject as she/he appears today. Your opinion should not be limited to the level of spasticity the subject is experiencing.

In other words, compared to her/his condition at Baseline, how much has she/he changed?

-3	Significantly worse compared to visit 2
-2	Moderately worse compared to visit 2
-1	Slightly worse compared to visit 2
0	No change
+1	Slightly improved compared to visit 2
+2	Moderately improved compared to visit 2
+3	Significantly improved compared to visit 2

Appendix 4. Patient Global Impression of Change Scale

PATIENT'S GLOBAL IMPRESSION OF CHANGE (PGIC) SCALE

Date _____ Patient Name _____ Date of Birth _____

Chief Complaint (Presenting Problem): _____

Since beginning treatment at this clinic, how would you describe the change (if any) in ACTIVITY LIMITATIONS, SYMPTOMS, EMOTIONS, and OVERALL QUALITY OF LIFE, related to your painful condition? Please circle the number below, that matches your degree of change since beginning care at this clinic for the above stated chief complaint.

No change	Almost the same	A little better	Somewhat better	Moderately better	Better	A great deal better
1	2	3	4	5	6	7

Explanation:

- 1 = No change (or condition has got worse)
- 2 = Almost the same, hardly any change at all
- 3 = A little better, but no noticeable change
- 4 = Somewhat better, but the change has not made any real difference
- 5 = Moderately better, and a slight but noticeable change
- 6 = Better, and a definite improvement that has made a real and worthwhile difference
- 7 = A great deal better, and a considerable improvement that has made all the difference

Patient's signature: X _____

Do not write in this box - FOR OFFICE USE ONLY.

NOTE TO HEALTH CARE PROVIDER

A significant, favorable change is a score of 5- 7
No significant change is a 1-4 response.
Note, this is a dichotomous scale (5-7 = yes; 1-4 = no).
A 2-point change is significant from their last reported score.
Reference: Hurst H, Bolton J. Assessing the clinical significance of change scores recorded on subjective outcome measures. Journal of Manipulative Physiological Therapeutics (JMPT) 2004;27:26-35.

[figure not shown]

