8.3 Patient Global Impression of Change

The PGIC is a standard instrument that is a well validated outcome measure. The 7-point PGIC measures change in the subject's overall status using the following categorical scale:

- 1 = Very much improved
- 2 = Much improved
- 3 = Improved
- 4 = No change
- 5 = Minimally worse

- 6 = Much worse
- 7 = Very much worse

The PGIC will be done at the visits specified in Table 1. The PGIC is provided in Appendix 4.

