5.3. Analysis Variables

Variables to be analyzed include demographics and baseline characteristics, safety variables (adverse events, clinical laboratory investigations, vital signs, ECGs, USP questionnaire, and C-SSRS), and efficacy variables (TNmAS-MAL, CGIC, PGIC, EDSS, and TNmAS-TL). See Section 8 of the protocol for further details on the efficacy variables. Derived variables from study endpoints are described with the sections describing the analyses for these endpoints.

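### The protocol defines PGIC on two seven-point scales that run in opposite directions, and the SAP states neither the coding nor which sign means benefit

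*Protocol*

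**What the plan says.** Protocol Section 8.3 lists seven PGIC categories. Code 1 is the best outcome, 4 is unchanged, and worsening begins at "5 = Minimally worse" and ends at 7. The section then states "The PGIC is provided in Appendix 4".

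Appendix 4 prints another seven-point list. It opens with "1 = No change (or condition has got worse") and rises to 7 for the largest improvement. Its scoring box says "A significant, favorable change is a score of 5- 7" and adds "Note, this is a dichotomous scale (5-7 = yes; 1-4 = no"). The stem reads "Since beginning treatment at this clinic, how would you describe the change (if any") and ties the answer to a painful condition.

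SAP 5.3 gives no PGIC code list; it says "See Section 8 of the protocol for further details on the efficacy variables". SAP 9.2.2 applies the CGIC repeated-measures model to PGIC and is silent on coding and direction. PGIC is listed as a secondary efficacy endpoint in protocol 11.4.2 and in SAP 4.2.2 and 9.2.1.

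**The concern.** The section that defines the endpoint and the form it points to disagree on what each number means. SAP 9.2.2 compares mean PGIC scores between each AERT dose and placebo. The sign of that difference carries the conclusion, and the documents allow both readings of it.

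There is also a loss of content. Section 8.3 has three separate codes for patients who got worse; Appendix 4 has none. If the Appendix 4 form is used, deterioration on any arm is recorded as no change. PGIC is the only patient-rated measure among the listed efficacy endpoints, so this information is not recovered from another efficacy endpoint.

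**Working it through.** No stated sample size, power or alpha figure underlies this point, so there is nothing to reproduce. The check sets the passages side by side, with labels paraphrased.

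| Code | Protocol 8.3 | Protocol Appendix 4 |
|---|---|---|
| 1 | greatest improvement | unchanged or worse |
| 2 | marked improvement | practically unchanged |
| 3 | improvement | small gain, not noticeable |
| 4 | unchanged | some gain, no real difference |
| 5 | slight worsening | moderate, noticeable gain |
| 6 | marked worsening | definite, worthwhile gain |
| 7 | greatest worsening | largest gain |

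**Direction.** The favorable codes are {1, 2, 3} in Section 8.3 and {5, 6, 7} in Appendix 4. Codes classed differently are {1, 2, 3, 5, 6, 7}, which is 6 of 7. Code 4 is not favorable on either.

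**Does reversal repair it?** Replacing the 8.3 score by 8 minus the score moves its favorable codes to {5, 6, 7}, so no favorable-class mismatch remains. The lower half still differs: unchanged becomes 8 − 4 = 4, against 1 on Appendix 4, and the three worsening codes become 1, 2 and 3, where Appendix 4 has unchanged or worse, practically unchanged, and a small gain. Appendix 4 code 1 covers both no change and every degree of worsening, so its data cannot be mapped back to 8.3.

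**Does the SAP settle the direction through CGIC?** No. Protocol Appendix 3 scores CGIC from −3 to +3, with +3 meaning "Significantly improved compared to visit 2", so higher is better. The penalty analysis in SAP 9.1.3 labels CGIC values 1, 2 and 3 in falling order of improvement, with 1 the best. Those labels match the improvement end of Section 8.3's PGIC list, not Appendix 3. The borrowed model therefore has an inconsistent direction of its own.

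**Illustration of the sign change.** The response distributions below are assumed; they are not document figures. From greatest worsening to greatest improvement:

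- Placebo: 0.02, 0.05, 0.13, 0.40, 0.25, 0.10, 0.05
- Active: 0.02, 0.04, 0.09, 0.30, 0.28, 0.17, 0.10

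Mean on Section 8.3 codes (7 down to 1):

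- Placebo: 0.14 + 0.30 + 0.65 + 1.60 + 0.75 + 0.20 + 0.05 = 3.69
- Active: 0.14 + 0.24 + 0.45 + 1.20 + 0.84 + 0.34 + 0.10 = 3.31
- Difference, active minus placebo: 3.31 − 3.69 = −0.38

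Three assumed mappings of the same seven states to Appendix 4 codes:

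| Assumed Appendix 4 codes | Placebo mean | Active mean | Difference |
|---|---|---|---|
| 1, 1, 1, 1, 3, 5, 7 | 2.20 | 2.84 | +0.64 |
| 1, 1, 1, 1, 4, 6, 7 | 2.55 | 3.29 | +0.74 |
| 1, 1, 1, 2, 3, 5, 6 | 2.55 | 3.04 | +0.49 |

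The same benefit is negative on one scale and positive on the other. If the Appendix 4 favorable range were applied to 8.3 codes, the patients counted as favorable would be those who worsened: 0.02 + 0.04 + 0.09 = 15% on active and 0.02 + 0.05 + 0.13 = 20% on placebo.

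**Visit (side point).** The schedule tables place PGIC, and EDSS after baseline, only at Visit 6 (nominal Day 92; 9 + 75 + 7 = 91 days of titration, maintenance and taper). SAP 9.2.2 compares arms at every visit that has data, so the scheduled comparison is at Visit 6. The borrowed models name Visits 4 and 5. The nearest-visit rule in SAP 7.3.3 does not say whether it counts any study visit or only visits where the measure is scheduled. A PGIC taken at early termination on Day 50 is 8 days from Visit 4, 34 from Visit 5 and 42 from Visit 6, so the reading matters.

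**The case against.** The strongest reply is that this is one secondary endpoint outside the testing sequence, that the case report form is not among the documents, and that the sites may have used a single form throughout. The 6 of 7 count mostly reflects reversal and disappears for the favorable codes once the score is flipped. All of that stands. It limits the severity but does not remove the contradiction: both lists are fully legible, neither redaction nor PDF reading explains the difference, and no passage says which one governs.

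Some stronger readings are tempting, and the documents do not support them.

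- *A reader might infer that the analysis visit and early-termination rule for PGIC and EDSS are missing.* They are not. The visit follows from the schedule tables and SAP 9.2.2, the Visit 6 column covers early termination, and SAP 7.3.3 states a general rule. Only its application to these two measures is unclear.
- *A reader might infer that PGIC inherits a fixed higher-is-better direction from CGIC.* SAP 9.1.3 contradicts Appendix 3 on that direction, so the inference fails.
- *A reader might take the dichotomous note in Appendix 4 as a conflicting analysis rule.* It sits in an office-use box on the form; the SAP governs the analysis and models the scores.
- *A reader might fault Appendix 4 alone for not anchoring to Visit 2.* Section 8.3 names no reference visit either; only CGIC does.

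Making the 8.3 labels symmetric is a design preference and is not needed to remove the conflict.

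**Conclusion.** The contradiction holds and should be fixed. As written, the sign of the AERT-minus-placebo PGIC difference cannot be interpreted from the protocol and SAP, and data collected on the Appendix 4 form cannot be converted to the Section 8.3 categories. This rests on the text alone; the −0.38 and the +0.49 to +0.74 are illustrations under assumed distributions and mappings. The effect on the actual PGIC result cannot be sized, and which form was administered is unknown.

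The reach is limited. TNmAS-MAL, CGIC, TNmAS-Total Limbs and the success criterion in SAP 7.5 do not depend on the PGIC scale. It would go too far to conclude that the PGIC result will be reported in the wrong direction: the documents show only that they do not fix the direction. The visit question is an optional clarification.

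**What to change.** Use one PGIC instrument in protocol Section 8.3, Appendix 4 and the case report form. The 8.3 categories can record worsening; the Appendix 4 form cannot. State in SAP 9.2.2, before unblinding, the numeric coding and which sign of AERT minus placebo means benefit.

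If the Appendix 4 form has already been administered, state its coding, state that it does not separate worse from unchanged, and do not pool its data with data from another version.

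Optional: add a sentence to SAP 7.3.3 saying how the nearest-visit rule applies to PGIC and EDSS, whose only scheduled post-baseline visit is Visit 6.

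Cost: a small protocol amendment, needing sponsor and IRB/IEC approval under protocol 12.2, a short SAP change, and one corrected form with any translations it needs. The documents do not say whether enrolment has begun; if it has, changing the form would leave two PGIC versions to report separately. The optional sentence is SAP text only.
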